6. STATISTICAL CONSIDERATIONS AND ANALYSIS PLAN

Primary and secondary efficacy analyses will include all patients who were included in the randomization. Final analysis will be performed after last patient, last visit (LPLV) and subsequent data cleaning, with patients allocated to the treatment arm associated by randomization.

Safety analyses will include all patients who were included in the randomization and received at least one dose of study treatment, with patients allocated to the treatment arm associated with the regimen actually received.

6.1 DETERMINATION OF SAMPLE SIZE

This study is designed for testing the effect of GDC-0032 on the two co-primary endpoints in all enrolled patients and in the *PIK3CA* MT patients and plans to enroll 330 patients in total. Assuming the *PIK3CA* mutation status will not be available (unknown) for approximately 10% of the patients and the prevalence of *PIK3CA* mutant is 40%, there will be approximately 120 patients in the *PIK3CA* MT cohort.

Given that the *PIK3CA* mutation status is not a stratification factor for randomization, there might be a possible imbalance between treatment arms within the *PIK3CA* MT cohort, which may reduce the statistical power in this cohort. To ensure the study provides sufficient statistical power even when the treatment assignment is imbalanced, the sample size was calculated based on a conservative scenario by assuming that the treatment assignment imbalance in *PIK3CA* MT is 40% vs. 60%. The sample size was calculated based on a chi²-test using continuity correction (Ury and Fleiss 1980).

To control an overall, two-sided, family-wise error rate under 20%, we use a two-sided significance level of 16% and 4% for the co-primary endpoints MRI ORR, and pCR, respectively.

Assuming 10% of the patients are unevaluable for the MRI ORR, approximately 300 enrolled patients and 108 patients in the *PIK3CA* MT cohort will be evaluable for analyses. This sample size allows us to detect an absolute percentage increase of 24% in MRI ORR rate in the GDC-0032 plus letrozole arm (64%) versus the letrozole-only arm (40%; Smith et al. 2005; Ellis and Ma 2007) in the *PIK3CA* MT cohort at 80% power and 16% two-sided significance level. The minimal detectable difference for ORR is approximately 15%.

Assuming that all patients are evaluable for pCR (i.e., approximately 330 enrolled patients and 120 in the *PIK3CA* MT cohort), this sample size provides 80% power to detect an absolute percentage increase of 18% in pCR in the GDC-0032 plus letrozole arm (19%) versus the letrozole-only arm (1%, Smith et al. 2005; Ellis and Ma 2007) in the *PIK3CA* MT cohort at the 4% two-sided significance level. The minimal detectable difference for pCR rate is approximately 13%.

If the prevalence of the *PIK3CA* mutation is lower than assumed, if there is more substantial treatment assignment imbalance in the *PIK3CA* MT cohort than assumed, or there is an increased number of unevaluable patients for the MRI ORR, the sample size may be increased to obtain the level of power at 80%, and the enrollment may be limited to patients with *PIK3CA* MT.

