6.4 EFFICACY ANALYSES

The primary and secondary efficacy analyses will include the ITT population; that is, all randomized patients will be included in the analyses, with patients grouped according to the treatment assigned at randomization.

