6.4.1 Primary Efficacy Endpoint

The co-primary efficacy endpoints are (1) tumor ORR, assessed by modified RECIST criteria by breast MRI and (2) the rate of pCR in breast and axilla (total pCR) after completion of study drug.

The tumor ORR will be calculated by treatment arm in all enrolled population and in *PIK3CA* MT population. Within each population, the ORR for the two treatment arms will be compared at a two-sided alpha of 16% using a Cochran Mantel-Haenszel test, stratified by tumor size and nodal status. The pCR rate will also be calculated and compared at a two-sided alpha of 4% based on the same analytical approach as ORR. The two alpha values account for a family-wise type I error rate of 20%. Patients with early study termination and hence missing efficacy outcome will be considered as non-responders.

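### MRI ORR power is computed on 108 evaluable PIK3CA mutant patients, but the primary analysis keeps about 120 with missing as non-response; on that basis the plan's own formula gives about 77%, not 80%

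*Protocol*

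**What the plan says.** Section 6.1 of the protocol, repeated in the synopsis under Statistical Methods, expects that "there will be approximately 120 patients in the *PIK3CA* MT cohort". For the two co-primary endpoints "we use a two-sided significance level of 16% and 4% for the co-primary endpoints MRI ORR, and pCR, respectively". For MRI ORR it then makes a deduction: "Assuming 10% of the patients are unevaluable for the MRI ORR, approximately 300 enrolled patients and 108 patients in the" mutant cohort are left for analysis. On those 108 it claims to detect 64% against 40% "at 80% power and 16% two-sided significance level". The calculation uses a chi-square test with continuity correction and, as a deliberately conservative scenario, a 40:60 split between arms within the mutant cohort.

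The analysis sections make no such deduction. Section 6 bases the primary efficacy analysis on everyone randomised, and section 6.4 repeats that "all randomized patients will be included in the analyses". Section 6.4.1 adds: "Patients with early study termination and hence missing efficacy outcome will be considered as non-responders". The test named there is a stratified Cochran-Mantel-Haenszel (CMH) test at two-sided 16%; no continuity correction is mentioned.

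**The concern.** Two different ORR analyses are described. Section 6.1 removes patients without a usable MRI. Sections 6, 6.4 and 6.4.1 keep them in the denominator, where they cannot count as responses.

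The explicit non-responder rule names early termination only. For a patient who completes but whose scan cannot be read, non-response follows by implication. Section 3.3.4 takes ORR as partial plus complete responses, Appendix 3 labels such a patient not evaluable, and the intention-to-treat denominator still includes her.

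The larger denominator helps power, but missing data counted as non-response shrink both rates and the difference between them. Section 6.1 reflects neither effect. At stake is whether the stated 80%, for the endpoint that carries 16 of the 20 percentage points of alpha, describes the analysis that will be run.

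**Working it through.** **Inputs, all from section 6.1 unless noted.** Alpha 0.16 two-sided, so z = 1.405. Rates 0.64 and 0.40. Mutant cohort about 120 (330 × 0.90 × 0.40 = 118.8). Unevaluable share 10%, so 120 × 0.90 = 108. Split 40:60, taken with control as the smaller arm. Continuity correction applied. All randomised patients kept (6.4); missing counted as non-response (6.4.1).

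**Formula.** Power = Φ[(d − c − z·s0) / s1], where
- d is the difference in rates;
- c = 0.5(1/n0 + 1/n1) is the continuity correction;
- s0 is the standard error using the pooled rate;
- s1 is the standard error using the separate rates.

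**Step 1: the plan's own figure.** n0 = 43.2, n1 = 64.8, d = 0.24, c = 0.0193, s0 = 0.0978, s1 = 0.0955.
Φ[(0.24 − 0.0193 − 1.405 × 0.0978) / 0.0955] = Φ(0.872) = about 81%. The required total for 80% is about 107. The stated 80% on 108 reproduces, which confirms how it was obtained.

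**Step 2: the analysis as written, equal missingness.** Rates become 0.64 × 0.90 = 0.576 and 0.40 × 0.90 = 0.360, so d = 0.216. With n0 = 48 and n1 = 72: c = 0.0174, s0 = 0.0932, s1 = 0.0905.
Φ[(0.216 − 0.0174 − 1.405 × 0.0932) / 0.0905] = Φ(0.749) = 77.3%. Exact enumeration of the corrected test gives 77.2%. With the split reversed (control 72) the formula gives 77.4%.

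**Step 3: how far this depends on the choices made.**

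| Basis | Corrected | Uncorrected |
|---|---|---|
| 108 evaluable, 64% vs 40%, 40:60 | 80.9% | 85.9% |
| 120, 57.6% vs 36.0%, 40:60 | 77.3% | 82.7% |
| 120, 57.6% vs 36.0%, 1:1 | 78.9% | 83.9% |
| 120, 64% vs 40% (if already intention-to-treat rates), 40:60 | 84.6% | 88.7% |

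For the second row, exact enumeration of the uncorrected test as a single unstratified table gives 83.3%. For the third row, the exact corrected figure is 79.9%. Corrected 40:60 power by missing share, equal in both arms: 5% gives 81.1%, 8% gives 78.8%, 10% gives 77.3%, 15% gives 73.3%.

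**Step 4: the minimal detectable difference.** Reading this as the smallest observed difference that reaches significance, with correction and 40:60, it is 15.7 points on 108 (control 40%) and 14.8 points on 120 (control 36%). Both fit the stated value of about 15%.

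**The case against.** The strongest reply is that nothing was miscalculated. The 80% follows from its stated inputs, and 77% arises only by carrying the planning formula's continuity correction over to the analysis. The planned test is a CMH test with no correction stated; uncorrected, the intention-to-treat power is about 83%, above target. The 40:60 split is also a deliberate worst case under 1:1 randomisation. All of this stands and limits the size of the point. It does not rescue the statement: 80% is the corrected figure for 108 evaluable patients, and neither version of the test gives it for the analysis in 6.4 at 40:60.

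A second reply is that 40% and 64% may already be intention-to-treat rates, since section 3.3.3 describes the ORR of the two cited neoadjuvant endocrine trials in that population. That is possible, and diluting them would then count missing data twice. But section 6.1 applies them to evaluable patients. If they are intention-to-treat rates, the deduction to 108 is unnecessary and power is about 85%, so the sections still disagree.

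Section 6.1 allows a larger sample if more patients than assumed are unevaluable. That does not cover dilution at the assumed 10%.

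A reader might go further and infer that the trial is underpowered and needs more patients: by the corrected formula at 40:60, 80% would take about 130 mutant patients. The documents do not support that, because the gap disappears with an uncorrected test. Nor do they support a claim that the detectable difference is wrong (step 4). Heavy loss of power from unequal dropout is likewise not shown. Missing shares of 12% on the active arm and 8% on control would give about 70% corrected, but those shares are hypothetical and appear nowhere in the protocol.

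**Conclusion.** The inconsistency between section 6.1 (with the synopsis) and sections 6, 6.4 and 6.4.1 is real, and the protocol fixes both sides of it. By the plan's own continuity-corrected formula at 40:60, the ORR power for the planned analysis is about 77% rather than 80%. This assumes that 64% and 40% are rates among evaluable patients, that the 10% is missing equally in both arms, and that unevaluable scans count as non-response along with early terminations. Under the same assumptions power is about 79% at 1:1 with correction, and about 83% at 40:60 without it. This is a mismatch of denominators with a modest, conditional effect on a stated figure. It calls the stated power into question, not the analysis, the sample size or the detectable difference.

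**What to change.** Keep the intention-to-treat analysis and restate the ORR power in section 6.1 and the synopsis on all of the approximately 120 mutant patients, with both rates diluted for the assumed 10% missing (57.6% versus 36.0%). Name whether the test is continuity-corrected: about 77% if it is, about 83% if not, at 40:60. If 64% and 40% are meant as intention-to-treat rates, say so and drop the reduction to 108; the corrected power is then about 85%.

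Unequal-dropout figures may be added only as a labelled hypothetical sensitivity. Redefining the primary ORR set as MRI-evaluable patients is not advised, since it would exclude patients on post-randomisation events. The cost is a few sentences in two places and, on the first route with the corrected test, a slightly less favourable power. No change to the primary analysis set or the sample size is needed.

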6.2 SUMMARIES OF CONDUCT OF STUDY

Enrollment, study treatment administration, and discontinuation from the study will be summarized overall and by treatment arm. The incidence of study treatment discontinuation for reasons other than disease progression will be tabulated.

6.3 SUMMARIES OF TREATMENT GROUP COMPARABILITY

Demographic variables, stratification factors, and other baseline characteristics will be summarized by treatment arm.

6.4 EFFICACY ANALYSES

The primary and secondary efficacy analyses will include the ITT population; that is, all randomized patients will be included in the analyses, with patients grouped according to the treatment assigned at randomization.

6.4.1 Primary Efficacy Endpoint

The co-primary efficacy endpoints are (1) tumor ORR, assessed by modified RECIST criteria by breast MRI and (2) the rate of pCR in breast and axilla (total pCR) after completion of study drug.

The tumor ORR will be calculated by treatment arm in all enrolled population and in *PIK3CA* MT population. Within each population, the ORR for the two treatment arms will be compared at a two-sided alpha of 16% using a Cochran Mantel-Haenszel test, stratified by tumor size and nodal status. The pCR rate will also be calculated and compared at a two-sided alpha of 4% based on the same analytical approach as ORR. The two alpha values account for a family-wise type I error rate of 20%. Patients with early study termination and hence missing efficacy outcome will be considered as non-responders.

6.4.2 Secondary Efficacy Endpoints

The secondary efficacy endpoints for this study are as follows:

- Tumor ORR after completion of study treatment, assessed by modified RECIST criteria by breast MRI in *PIK3CA* WT patients.
- Rate of pCR in breast and axilla (total pCR) after completion of study drug in *PIK3CA* WT patients.
- These endpoint measures will be summarized by treatment arm and will be analyzed analogue to the primary efficacy endpoint.
- The following secondary efficacy endpoints will be performed in all enrolled patients and separated by *PIK3CA* mutation status:
 - ORR by clinical breast examination, mammography, and breast ultrasound
 - Ki67 values at baseline, Week 3, and surgery (centrally assessed)
 - Change in Ki67 from baseline to Week 3; baseline to surgery, and Week 3 to surgery (centrally assessed)
 - PEPI score (centrally assessed)
 - Change in enhancing tumor volume from baseline to surgery as measured by breast MRI

- Evaluation of different definitions of pCR including the following: a) ypT0, ypN0, and b) ypT0/is, ypNX (breast pCR)

These endpoint measures will be summarized by treatment arm and will be compared between the two treatment arms within each population based on appropriate statistical analyses: ORR will be compared using a Cochrane Mantel-Haenszel test, stratified by tumor size and nodal status; PEPI, Ki67, and tumor volume change will be compared by regression analyses, adjusted for tumor size and nodal status. All secondary endpoints will be tested at a two-sided type I error of 5%.

More details of the analyses will be provided in the Statistical Analysis Plan (SAP).

6.5 SAFETY ANALYSES

Safety analyses will include all patients who received at least one dose of study treatment, with patients allocated to the treatment arm associated with the regimen actually received.

Safety will be assessed through summaries of adverse events, changes in laboratory test results, changes in vital signs, and letrozole and GDC-0032 exposure.

Verbatim descriptions of adverse events will be mapped to thesaurus terms. Adverse event data will be listed by study site, treatment arm, patient number, and study day, severity, relationship to study drug, outcome, and action taken with the study treatments. Events occurring on or after treatment on Day 1 of Week 1 will be summarized by thesaurus term, appropriate thesaurus levels, and NCI CTCAE v4.0 grade. Serious adverse events, including deaths, will be listed separately and will be summarized.

Relevant laboratory and vital sign (heart rate, blood pressure, and temperature) data will be displayed by time, with NCI CTCAE v4.0 Grade 3 and 4 values identified, where appropriate. Additionally, all laboratory data will be summarized in tables by NCI CTCAE v4.0 grade.

6.6 PHARMACODYNAMIC ANALYSES

Ki67 biomarker analyses will include patients with at least one predose and one postdose biomarker assessment, with patients grouped according to the treatment actually received.

6.7 PHARMACOKINETIC ANALYSES

Individual C_{max} and trough plasma concentrations (C_{min}) of GDC-0032 and letrozole from all patients enrolled will be reported. Mean of trough plasma concentrations of GDC-0032 and letrozole will be tabulated. The population pharmacokinetics of letrozole and GDC-0032 in this study will be compared with historical single-agent pharmacokinetics to assess the potential DDI between GDC-0032 and letrozole in this population.

Additional PK analyses on metabolites of GDC-0032, letrozole, and/or other concomitant medications may be conducted as appropriate.

6.8 PATIENT-REPORTED OUTCOME ANALYSES

Patient-reported outcomes of breast cancer symptoms, patient functioning, and HRQoL will be assessed by the EORTC QLQ-C30 and the modified Breast Cancer module (QLQ-BR23)

Summary statistics (mean, standard deviation, median and range) of linear transformed scores will be reported for all the items and subscales of the EORTC QLQ-C30 questionnaire, and the modified QLQ-BR23 according to the EORTC scoring manual guidelines for each assessment time point. The mean change of the linear transformed scores from baseline (and 95% CI using the normal approximation) will also be assessed. Line charts depicting the mean changes (and standard errors) of items and subscales over time will be provided for each treatment arm from the baseline assessment.

Data analysis will be performed on the final modified BR23 data set in parallel with the final data analysis to assess the psychometric properties of the modified instrument and will be reported along with the clinical trial results.

Completion and compliance rates will be summarized at each timepoint by treatment arm with reasons for missing data. Only patients with a baseline assessment and at least one post-treatment assessment will be included in the analyses. The number and proportion of patients who improved, worsened, or remained stable for all of the symptom and functional domains, global QoL, and single items of the EORTC QLQ-C30 and QLQ-BR23 will be summarized.

6.9 EXPLORATORY ANALYSES

Additional details on analyses will be specified in the SAP.

6.10 INTERIM ANALYSES

The IDMC will conduct interim analyses to review the unblinded safety data after the first 20 patients have either 1) finished the 30-day, follow-up visit after the surgery, or 2) been on study for 20 weeks after the randomization date (for those who do not receive the surgery). All available information of all enrolled patients with all available assessments at the respective timepoint will be included in the interim analyses. In addition, the IDMC or the Medical Monitor may request additional ad hoc meetings of the IDMC at any time during the study to review safety data.

7. DATA COLLECTION AND MANAGEMENT

7.1 DATA QUALITY ASSURANCE

ABCSG will be responsible for data management of this study, including quality checking of the data. Data entered manually will be collected via EDC using eCRFs. Sites will be responsible for data entry into the EDC system. In the event of discrepant data, ABCSG and/or all involved clinical research associates (CRAs) will request data clarification from the sites, which the sites will resolve electronically in the EDC system.

ABCSG will produce a Data Management Plan that describes the quality checking to be performed on the data. The Sponsor will perform oversight of the data management of this study, including review of the ABCSG's data management plan and corresponding specifications. Data will be transferred electronically from ABCSG to the Sponsor at the end of the study and whenever otherwise contractually agreed, and the Sponsor's standard procedures will be used to handle and process the electronic transfer of these data.

eCRFs and correction documentation will be maintained in the EDC system's audit trail. System backups for data stored at ABCSG and records retention for the study data will be consistent with the ABCSG's standard procedures.

Data from paper PRO questionnaires will be entered into the EDC system by site staff. Original PRO questionnaires will be kept in the patient's medical record as source documentation.

7.2 DATA(BASE) MANAGEMENT

ABCSG Clinical Data Management will check all e-forms for plausibility and consistency by automatic edit checks and manual data review according to study-specific data management plan (DMP). If necessary, web-based data queries (data clarification requests [DCRs]) will be generated and subsequently visible for the investigators, dedicated site staff, responsible CRAs, and responsible ABCSG staff. For those eCRFs which pass all verification procedures and are regarded as correct and complete, they will be frozen subsequently by ABCSG clinical data management. Consequently, no further data entries or changes on frozen eCRFs are possible. The status of frozen eCRFs is flagged by the specific icon.

Clinical Data Management ensures that the database is corrected for the following eCRF issues without immediate notification to site staff (self-evident corrections). Notification of site staff is provided via a specific report after final data cleaning procedures and before final data confirmation by the investigator or a designee:

- misspellings/typing errors that do not change the meaning of the word
- location of data recorded at an incorrect variable field or eForm (e.g., moving lab data from general comments to the appropriate lab table)

- standard time to 24-hour clock
- correction of date format, if required (dd/mm/yyyy)
- if equivalent units of terms are recorded instead of the acceptable ABCSG standard
- data changes due to plausibility checks and eCRF content (e.g., combination of several variables and/or eCRFs)

All data management workflows are described in detail in the relevant SOPs and working instructions of ABCSG.

7.3 ELECTRONIC CASE REPORT FORMS

eCRFs are to be completed using the Clinical Data Management System “MACRO,” a web-interface DATAPORT. Sites will receive training by the responsible CRAs and have access to a manual for appropriate eCRF completion (web data entry).

All eCRFs should be completed by designated, trained site staff in a timely manner, usually within 2 weeks after the patient visit. Electronic CRFs should be reviewed and respective data confirmation eCRF should be electronically signed and dated by the investigator or a designee at the end of the study.

At the end of the study, the investigator will receive patient data for his or her site in a readable format on a storage medium (compact disc [CD], digital video disk [DVD] etc.) that must be kept with the study records. Acknowledgement of receipt of the storage medium is required.

7.4 SOURCE DATA DOCUMENTATION

Study monitors (CRAs) will perform ongoing SDV to confirm that critical protocol data (i.e., source data) entered into the eCRFs by authorized site personnel are accurate, complete, and verifiable from source documents.

Source documents (paper or electronic) are those in which patient data are recorded and documented for the first time. They include, but are not limited to, hospital records, clinical and office charts, laboratory notes, memoranda, patient-reported outcomes, evaluation checklists, pharmacy dispensing records, recorded data from automated instruments, copies of transcriptions that are certified after verification as being accurate and complete, microfiche, photographic negatives, microfilm or magnetic media, X-rays, patient files, and records kept at pharmacies, laboratories, and medico-technical departments involved in a clinical trial.

Before study initiation, the types of source documents that are to be generated will be clearly defined in the Trial Monitoring Plan. This includes any protocol data to be entered directly into the eCRFs (i.e., no prior written or electronic record of the data) and considered source data.

Source documents that are required to verify the validity and completeness of data entered into the eCRFs must not be obliterated or destroyed and must be retained per the policy for retention of records described in [Section 7.6](#).

To facilitate SDV, the investigators and institutions must provide the Sponsor/CRA direct access to applicable source documents and reports for trial-related monitoring, Sponsor audits, and IRB/EC review. The investigational site must also allow inspection by applicable health authorities.

